#### 1. INTRODUCTION

Genomic instability is a hallmark of cancer, arising from a combination of replication stress and errors in DNA damage response (DDR). DDR deficiency (DDR-D) enables the cancer cell's acquisition of driver gene mutations but also engenders targetable vulnerabilities to treatment strategies that induce insurmountable DNA damage, such as platinum chemotherapies, and/or further suppress DDR leading to catastrophic instability. In addition, multiple pre-clinical and clinical studies have shown significant cross-talk between DDR-D, tumor immune infiltrate, and response to immuno-oncology agents (IO) . Thus, identifying DDR aberrations in cancers is extremely important for therapeutic decision making with the advent of immune checkpoint blockade and new classes of DDR inhibitors (DDRi), such as poly (ADP-ribose) polymerase (PARP) inhibitors (PARPi), ataxia telangiectasia mutated and rad3-related (ATR) inhibitors (ATRi). Multiple PARPi are FDA-approved for the treatment of recurrent BRCA1/2 mutant ovarian cancers, as well as BRCA1/2 mutant breast cancers. However, the clinical response to PARPi and DNA damaging agents such as platinum-based chemotherapies, is limited by almost inevitable drug resistance, culminating in short-lived antitumor responses. Therefore, there remains a significant unmet clinical need for novel antitumor strategies beyond just PARPi and platinum to increase the depth and duration of response, and survival benefits for patients with advanced cancers harboring DDR aberrations.

#### 1.1 Mechanisms of Action/Indication

### 1.1.1 Avelumab, PD-L1 immune checkpoint inhibitor

Avelumab is an immune checkpoint-blocking antibody which targets programmed death ligand 1 (PD-L1), thereby disrupting the interaction with and signaling through the programmed death receptor 1 (PD-1), resulting in activation of T cells. Clinically, avelumab is approved for patients with Merkel cell carcinoma and for patients with locally advanced or metastatic urothelial carcinoma following disease progression during or after platinum-based chemotherapy, or within 12 months of neoadjuvant or adjuvant platinum-based chemotherapy. Ongoing clinical studies have demonstrated meaningful clinical activity across multiple tumor types and treatment settings, with ongoing responses > 1 year (NCT01772004, JAVELIN Solid Tumor).

### 1.1.2 M6620, ATR inhibitor (formerly VX-970)

M6620 is a first in class, potent inhibitor of ataxia telangiectasia mutated and Rad3-related protein (ATR). Supporting pre-clinical studies have demonstrated that PARPi-resistant *BRCA1*-deficient cells are exquisitely dependent on ATR for survival; ATR inhibitors (ATRi) disrupt BRCA1-independent RAD51 loading to DNA DSBs in PARPi-resistant *BRCA1*-deficient cells, overcoming such resistance mechanisms. ATRi may therefore potentially overcome PARPi-resistance in *BRCA*-deficient cancers. In addition, the ATR/CHK1 and ATM/CHK2 axes have multiple interconnected and overlapping functions in regards to DDR, cell cycle regulation, and mitigation of replication stress. Preclinical and early clinical studies of ATR inhibitors have shown functional loss of ATM to predict for ATR inhibitor sensitivity. Deficiency in ARID1A, a key chromatin regulator, have also been shown to lead to homologous repair deficiency (HRD) and in particular susceptibility to ATR inhibition in preclinical models. Other pre-clinical *in vitro* studies have demonstrated that M6620 sensitizes many cancer cell lines to the cytotoxic effects of numerous DNA-damaging drugs. *In vivo*, M6620 has also been shown to potentiate the antitumor activity

of DNA-damaging agents and radiotherapy. For example, in patient-derived xenograft mouse models of non-small cell lung cancer (NSCLC), the combination of M6620 with cisplatin resulted in significantly greater tumor control in comparison to either single agent¹². Additionally, in a xenograft mouse model of gastric cancer, treatment with the ATRi AZD6738, decreased proliferation (by Ki67 expression) and increased apoptosis (by TUNEL assay), resulting in greater tumor control¹³. In a recent phase I clinical trial, the combination of M6620 and Topotecan, was demonstrated to be active in platinum-refractory small-cell lung cancer (SCLC), which is notably resistant to Topotecan monotherapy. Partial response or prolonged stable disease (≥ 6 months) was observed in 3 of 5 SCLC patients enrolled in this study¹⁴. Additionally, phase I studies of M6620 led by [name], have also demonstrated promising clinical activity in patients harboring *BRCA1/2* mutant cancers¹¹⁵-17.

# 1.2 Rationale for the combination of DDR and immune checkpoint inhibitors

There is strong preclinical and clinical evidence that DDR-D and S-phase specific DNA damage leads to activation of innate immune pathway activity including the stimulator of interferon gamma (STING) axis, increased tumor immune infiltrate, increased PD-L1 expression, and improved response to immune therapy (IO). Preclinical data has also shown DDRi can have similar effects on PD-L1, innate immune activity, and immune response as genetic deficiencies in DDR. However, the clinical response to single-agent DDRi, including PARPi, is limited by drug resistance, with short-lived antitumor responses, even in tumors with DDR gene aberrations. In addition, single agent IO response is not uniform, even within a single tumor type, and predictive functional biomarkers are lacking. Therefore, there remains a significant unmet clinical need for novel antitumor strategies to increase the depth and duration of response to both IO and DDRi, and improve survival benefits for patients with advanced cancers harboring DDR aberrations. Recent preclinical data provide rationale to combine DDR inhibitors such as ATRi with immunotherapies in an effort to increase clinical outcomes for patients with cancers carrying mutations in DDR genes. In a study of DNA repair-deficient breast cancers, Parkes et al., identified a mechanism of immune response where STING-mediated chemokine production occurred in response to DNA damage. This resulted in an inflammatory microenvironment in DDR-deficient breast tumors. They also found that expression of PD-L1 was associated with tumors deficient in DDR, supporting the investigation of immunotherapies in tumors harboring DDR defects. Other studies have demonstrated that PARPi treatment can increase the expression of PD-L1 on breast cancer cells, and that the combination of PARPi and anti-PD-L1 therapy significantly increased antitumor response in mouse models of breast cancer in comparison to either monotherapy. In a Phase I modular study led by [name], the combination of the ATRi AZD6738 with the PD-L1-targeting antibody durvalumab, was shown to be well tolerated with signals of antitumor activity.

### 2. STUDY OBJECTIVES AND ENDPOINTS

# 2.1 Primary, Secondary, and Exploratory Objectives

#### 2.1.1 Arm A: M6620 + Avelumab

# **Primary Objectives:**

- 1. To determine the safety and tolerability of the combination of M6620 and avelumab in patients with DDR deficient advanced solid tumors.
- 2. To establish the maximum tolerated dose (MTD) and recommended phase 2 dose (RP2D) of the combination of M6620 and avelumab in patients with DDR deficient advanced solid tumors.

### Secondary objectives:

- To determine the clinical benefit of the combination as defined by clinical benefit rate (CBR) - complete response [CR] + partial response [PR] + stable disease [SD] > 6 months (CR+PR+SD>6months).
- To assess clinical benefit of the combination as defined by objective response rate (ORR), overall survival (OS), duration of response (DoR) and progression free survival (PFS). Patients will be followed for 6 months after a confirmed response.

### **Exploratory objectives:**

- 1. To evaluate clinical benefit of the combination of M6620 and avelumab based on specific DDR aberrations.
- 2. To evaluate clinical benefit of the combination of M6620 and avelumab based on DDR gene expression signatures.
- 3. To evaluate the impact of treatment on PD-L1 expression and immune cell populations.
- 4. To assess potential mechanisms of resistance by comparing pre- and on-treatment biopsies in responders and non-responders.
- 5. To evaluate the pharmacokinetic (PK) and pharmacodynamic (PD) profile of M6620 in combination with avelumab in patients with DDR deficient advanced solid tumors

## 2.2 Primary, Secondary, and Exploratory Endpoints

#### 2.2.1 Arm A - M6620 + Avelumab

# **Primary Endpoints:**

- 1. Incidence and severity of adverse events (AEs) and serious adverse events (sAEs) (as graded by NCI CTCAE version 5.0), including significant changes in laboratory parameters, ECGs, and vital signs.
- 2. Incidence of dose-limiting toxicities (DLTs) (see Section 3.3).

### **Secondary Endpoints:**

- 1. Clinical benefit will be assessed radiographically per Response Evaluation Criteria in Solid Tumors (RECIST) version 1.1, and immune-related RECIST (irRECIST).
- 2. ORR, OS, DOR and PFS by radiographic disease assessments per RECIST v1.1 and irRECIST.

# **Exploratory Endpoints:**

- 1. Correlation between clinical benefit (CBR, ORR, PFS, DOR or OS), and ATM mutations and/or protein loss.
- 2. Assessment of homologous recombination deficiency (HRD) score and replication stress response defect (RSRD) score.
- 3. Immunohistochemistry, immunofluorescence, and flow cytometry analysis of immune cell subsets and markers.
- 4. Whole exome sequencing, RNA-sequencing, and Reverse Phase Protein Array (RPPA) analysis of pre-, on-treatment, and optional at-progression tumor biopsies.
- 5. PK summary statistics, concentration-time profiles and parameters (e.g. CL, AUC,  $C_{max}$ ,  $T_{max}$ , half-life if estimable)

### 3. STUDY DESIGN

### 3.1 Study Overview

This is a single-center, investigator-initiated, open-label, study of M6620 in combination with avelumab (Arm A), in adult patients with advanced solid tumors with aberrations in DNA Damage Response (DDR) genes.

[figure not shown]
Note: Additional arms will be developed based on evolving molecular and clinical data, and will be added to this protocol following a substantial amendment.

This is an adaptive program of trials, which will be set up sequentially depending on the development and/or availability of the individual agents. In this adaptive study, patients with DDR deficient biomarker positive advanced solid tumors entered on study may crossover to other available combination baskets upon disease progression, depending on evolving molecular and/or immune profiling data.

The number of patients in each basket may be increased depending on pre-defined signals and early stopping rules for futility or toxicity as described in Section 3.2 and Section 9.6. Patients will have pre and on-treatment tumor biopsies for correlative translational studies described in Section 7.5. All patients will have serial testing of blood parameters for DDR aberrations (e.g. ctDNA) and immune profiling.

### 3.2 Study Treatment Arms

Figure 1: DNA Damage Repair (DDR) Inhibitor-based Basket of Baskets Trial (D-BoB)

# ARM A: Dose Escalation and Expansion of M6620 + Avelumab

# Dose Escalation for Arm A

- Patients with advanced solid tumors harboring DDR defects
- Intrapatient dose escalation will be allowed

Dose Levels	Dose, frequency, route of administration
Dose Level 2	M6620: 480 mg/m  , QW, IV; Avelumab: 800 mg, Q2W, IV
Dose Level 1 (starting dose)	M6620: 240 mg/m², QW, IV; Avelumab: 800 mg, Q2W, IV
Dose Level -1	M6620: 120 mg/m  , QW, IV; Avelumab: 800 mg, Q2W, IV

# Dose Expansion for Arm A

- RP2D
- · Patients with advanced solid tumors harboring DDR defects
- N = 10 up to a maximum of 30 patients\*

\*Note: a 3-stage decision with 10 patients at each stage will be used for each regimen in the dose expansion phase of the trial. We will stop after the 1st stage if we see 0 successes in 10 patients,

after the 2nd stage if we see < 2 successes in 20 patients, and we will declare the treatment worthy of further study if we see > 3 successes in 30 patients.

QW = weekly; Q2W = every two weeks; MTD = Maximum Tolerated Dose; RP2D = Recommended Phase 2 Dose

#### 3.2.1 Arm A: M6620 + Avelumab

This basket study will begin with dose escalation and expansion of the combination of M6620 and avelumab. During the dose escalation phase, patients with advanced solid tumors who meet eligibility criteria may be treated at 1 of 3 doses of M6620 in combination with a fixed dose of avelumab, and will be evaluated for dose limiting toxicities (DLTs). Intrapatient dose escalation will be allowed in this trial.

Intra-patient dose escalation for patients enrolled in dose level 1 may be considered in consultation with the Principal Investigator. Once the respective dose level has been declared safe, patients who have completed at least 2 Cycles of treatment at the original enrolled dose level may escalate to the next higher dose level that has cleared the DLT observation period of 28 days. For the safety analysis, patients will be considered at both dose levels.

All patients must have DDR aberrant advanced solid tumors to be eligible. The dose expansion phase will be enriched for patients with advanced solid tumors with aberrations in the following DDR genes: ARID1A, ATM, ATR, ATRX, BAP1, BARD1, BRCA1/2, BRIP1, CDK12, CHEK2, FANCA, FANCC, FANCD2, FANCE, FANCF, FANCM, MRE11A, MSH2, NBN (NBS1), PALB2, RAD51, RAD51C, RAD51D, SMARCB1, and VHL. Other appropriate aberrations may be considered for patient selection at the discretion of the PI depending on emerging data. Variant interpretation for actionability will be performed by the MD Anderson Cancer Center (MDACC) Institute for Personalized Cancer Therapy (IPCT) Precision Oncology Decision Support (PODS) group. The PODS team facilitates a real-time mutation-by-mutation assessment of actionability. High-throughput literature retrieval from the MEDLINE database, along with natural language processing (NLP), is performed to identify scientific literature that potentially shed light on whether there is experimental evidence showing if a genomic alteration increases the cellular processes of tumorigenesis. The literature is then manually reviewed by expert scientists to validate and record the experimental assessment of each alteration.

Table 1: Dose Escalation of the combination of M6620 and avelumab (Arm A)

Dose Level	Dose, frequency, and route of administration
Dose Level 2	M6620: 480 mg/m  , QW, IV; Avelumab: 800 mg, Q2W, IV
Starting Dose Level 1	M6620: 240 mg/m  , QW, IV; Avelumab: 800 mg, Q2W, IV
Dose Level -1	M6620: 120 mg/m  , QW, IV; Avelumab: 800 mg, Q2W, IV

**Note:** other intermediate doses of M6620 may be considered following discussion with EMD Serono.

When avelumab and M6620 are to be administered on the same day, avelumab will be administered first, with an interval of at least 1 hour between infusions.

[figure not shown]

Figure 2: Dose Expansion of the combination of M6620 and avelumab (Arm A)

Interim Analysis for Safety: Patients can have any qualifying DDR aberration for interim safety analysis. We will stop if, at any time during the study, we determine that there is more than an 80% chance that the posterior probability of toxicity (i.e., DLT) is more than 30%.

2Interim Analysis for Futility: Using a 3-stage design with 10 patients in each stage, we will stop after the 1st stage if we see 0 successes in 10 patients, after the 2nd stage if we see <2 successes in 20 patients, and we will declare the treatment worthy of further study if we see >3 successes in 30 patients. If we set p0 (highest success rate for unacceptable treatment) =5% and p1 (lowest success rate for acceptable treatment) =20%, this design has alpha=5%, 80% power and probability of early termination under p0 of 60% after 1st stage and 79% after either 1st or 2nd stage.

Note: This study will not be rejected for efficacy until at least N=10 patients with ATM variants have been evaluated for efficacy.

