### 3.3 Dose Limiting Toxicity (DLT) Definition

Severity of adverse events will be graded according to the National Cancer Institute Common Terminology Criteria for Adverse Events (NCI CTCAE) version 5.0. A DLT is defined as any death not clearly due to the underlying disease or extraneous causes or as any Grade ≥ 3 non-hematologic AE or any Grade ≥ 4 hematologic AE according to the NCI-CTCAE v 5.0, occurring during the DLT observation period that is related to any of the study interventions as determined by the Investigator or Sponsor at any dose and judged not to be related to the underlying disease or any previous or concomitant medication. A DLT must be confirmed by the SMC.

Any of the following adverse events occurring in the first 28 days of study participation are considered DLTs:

- 1. Grade 4 neutropenia ≥ 7 days or febrile neutropenia will be considered dose limiting.
- 2. Grade 3+ thrombocytopenia with bleeding or Grade 4 thrombocytopenia >7 days will be considered dose limiting.
- 3. A study intervention-related TEAE that in the opinion of the Safety Monitoring Committee (SMC) is of potential clinical significance such that further dose escalation would expose participants to unacceptable risk.
- 4. Delay by more than 4 weeks (28 days) in receiving the next scheduled cycle of study drug(s) due to persisting toxicities attributable to the study drug(s).
- 5. Non-hematologic toxicities:
  - a. Grade ≥ 3 nausea/vomiting or diarrhea lasting ≥ 72 hours while receiving optimal supportive medications,
  - b. Grade  $\geq$  3 fatigue lasting  $\geq$  7 days,
  - c. Grade3 pneumonitis of any duration,
  - d. Grade  $\geq$  3 rash lasting  $\geq$  7 days despite treatment,
  - e. Any Grade 4 immune related toxicities
  - f. Any other Grade ≥ 3 non-hematological toxicity (except for electrolyte abnormalities that are reversible and asymptomatic or hair loss which is not dose-limiting; as well as Grade 3 infusion-related reaction of any duration,
  - g. AST or ALT >3 × ULN and concurrent total bilirubin >2 × ULN of any duration without initial findings of cholestasis (elevated alkaline phosphatase, e.g., findings consistent with Hy's law or FDA definition of potential IP-induced liver injury).. For patients with hepatic metastases: AST, ALT >8X ULN; AST or ALT >5X ULN lasting ≥14 days.

The following treatment-related AEs are exceptions to the above mentioned DLT definition and are **not** considered to be DLTs:

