### 3.5 Dose Escalation and Stopping Rules

The decision to proceed to the next dose level will be made after the first 3 patients in a dose level have completed 28 days (1 cycle) of dosing. Prior to advancing/changing dose levels, a dose

level summary will be completed and submitted to SMC for review and approval. The data discussed at the SMC during escalation/expansion phases and the minutes of the meetings will be submitted to the IND Office Medical Affairs & Safety group.

Figure 4: Dose Escalation Rules:

Dose escalation will occur at the planned dose levels until the MTD is determined. The MTD is defined as the highest dose level with less than two patients with DLT out of at least six patients. The recommended phase 2 dose (RP2D) will be based on the safety and preliminary efficacy data from the dose escalation and dose expansion arms. Intra-patient dose escalation will only be allowed if the patient experienced grade ≤1 AEs at the current dose.

All enrolled participants will be considered in the DLT analysis. If any patient should be excluded from the analysis, the reason(s) should be clearly documented (see Section 3.3). If a DLT occurs at a dose level with 3 patients within the first 28 days, 3 additional patients will be enrolled at that dose level. If at any time, at least one third of the participants at a dose level (33%) experience DLTs, the MTD will be reassessed and the next lowest dose level will be considered the MTD.

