# 9.1.2 DLT Analysis Set

The DLT analysis set is a subset of the safety analysis set and includes all enrolled patients in the dose escalation phase, receive at least one dose of the combination treatment, and either experience DLT during the first cycle (28 days) of treatment, or complete the DLT observation period for the first cycle of treatment.

Patients without DLTs who withdraw from study treatment before receiving at least 75% of the planned dose of each of the investigational products in the combination in Cycle 1 for reasons other than toxicity, which are attributable to the investigational products are not evaluable for DLT. Additional patients will be enrolled in the specific cohort to replace patients who are not considered DLT evaluable.

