# 9.3 Sample Size Determination

There will be 3-6 patients enrolled per dose level in the dose escalation phase of the combination of M6620 and avelumab.

Each dose expansion arm may have up to 30 patients each. A 3-stage design with 10 patients in each stage will be utilized. We will stop after the 1st stage if we see 0 successes in 10 evaluable patients on RP2D, after the 2nd stage if we see < 2 successes in 20 evaluable patients, and we will declare the treatment worthy of further study if we see > 3 successes in 30 evaluable patients. If we set p0 (highest success rate for unacceptable treatment) = 5% and p1 (lowest success rate for acceptable treatment) = 20%, this design has alpha = 5%, 80% power and probability of early termination under p0 of 60% after 1st stage and 79% after either 1st or 2nd stage.

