## 9.6.1 Safety Evaluation

Safety analyses will be conducted using the safety population. For the objective of describing the toxicity profile, descriptive statistics will be provided on the grade and type of toxicity by dose level.

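### The dose level 2 adverse event summary pools patients who escalated into that level with patients who started there, so it does not describe a new starter

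*Combined protocol and SAP*

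**What the plan says.** Four provisions bear on this point.

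- **Who may escalate.** Section 3.2.1 addresses patients enrolled at dose level 1: "patients who have completed at least 2 Cycles of treatment at the original enrolled dose level may escalate to the next higher dose level", provided that level has been declared safe and has cleared its 28-day DLT period. Section 3.5 adds: "Intra-patient dose escalation will only be allowed if the patient experienced grade ≤1 AEs at the current dose".
- **How they are counted.** Section 3.2.1: "For the safety analysis, patients will be considered at both dose levels".
- **How toxicity is reported.** Section 9.6.1, on the safety population: "descriptive statistics will be provided on the grade and type of toxicity by dose level". There is no split by starting dose and no adjustment for exposure. Section 9.6.2 counts a patient once per preferred term, at the highest severity, but does not say which level receives an AE that begins at one level and worsens or recurs at the next.
- **How DLTs are counted.** Section 3.3: "Any of the following adverse events occurring in the first 28 days of study participation are considered DLTs". The DLT analysis set in 9.1.2 takes escalation-phase patients who "either experience DLT during the first cycle (28 days) of treatment, or complete the DLT observation period for the first cycle of treatment". Sections 3.4 and 3.5 define the MTD by a count, fewer than two patients with DLT among at least six. Section 3.5 also has a separate rule, applied at any time: if "at least one third of the participants at a dose level (33%) experience DLTs, the MTD will be reassessed" and the next lower level is taken as the MTD.

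**The concern.** A patient who reaches dose level 2 by escalation differs from one who starts there in two ways. The escalator has been selected for having at most Grade 1 AEs, and has at least two cycles of prior exposure to both drugs. Counting both kinds of patient in one level-2 column gives a rate that belongs to neither group.

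The rate that informs a dose choice is the rate in patients who start at that dose, because expansion patients will start at the RP2D. AE incidence and severity is a primary endpoint (section 2.2.1), and section 3.5 bases the RP2D on safety and preliminary efficacy data. Study Calendar footnote 16 has expansion patients treated at the RP2D established in the escalation phase. The first choice is therefore made when cohorts are smallest and a few escalators weigh most.

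A second, narrower question is whether escalators enter the denominator of the one-third rule, which refers to participants at a dose level and not to a named analysis set.

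**Working it through.** **Inputs.** Section 9.3: "There will be 3-6 patients enrolled per dose level in the dose escalation phase". So about three to six level-1 patients could become escalators, at most. Six is an upper limit: if level 1 was enlarged because of a DLT, that patient would not meet the Grade 1 condition. The documents give no toxicity rate for level 2, for starters or for escalators, so there is no stated figure to reproduce and all rates below are assumptions.

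**Step 1: the by-level AE rate.** With n starters at rate q_s and m escalators at rate q_e:

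pooled rate = (n × q_s + m × q_e) / (n + m)

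For n = 6 and q_s = 40%:

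| q_e (assumed) | m = 3 | m = 6 |
|---|---|---|
| 0% | 2.4/9 = 26.7% | 2.4/12 = 20% |
| 10% | 2.7/9 = 30% | 3.0/12 = 25% |
| 20% | 3.0/9 = 33.3% | 3.6/12 = 30% |
| 40% | 3.6/9 = 40% | 4.8/12 = 40% |
| 60% | 4.2/9 = 46.7% | 6.0/12 = 50% |

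With six escalators at 10%, starter rates of 20%, 30%, 40% and 50% pool to 15%, 20%, 25% and 30%. The pooled rate understates the starter rate only when q_e is below q_s. It equals it when the rates agree and overstates it when escalators fare worse.

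**Step 2: after expansion.** If level 2 became the RP2D and all 30 expansion patients were treated there, n = 6 + 30 = 36. At 40% for starters and six escalators at 10%, the pooled rate is (36 × 0.40 + 6 × 0.10)/42 = 15.0/42 = 35.7%. The distortion then falls from 15 percentage points (40% to 25%) to about 4.

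**Step 3: DLT set and MTD count.** Escalators arrive after at least two 28-day cycles, 56 days. The DLT window is the first 28 days of study participation, and the DLT analysis set is built on the first cycle. By definition an escalator adds neither a DLT nor an evaluable patient at level 2. The MTD criterion is a count, so two DLTs fail it whether the denominator is 6, 9 or 12.

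**Step 4: the one-third rule.** This rule names no analysis set. If escalators were in the denominator, 2/6 = 33% would become 2/9 = 22% with three of them or 2/12 = 17% with six, and the number of DLTs needed would rise from 2 to 3 or 4. For six starters at an assumed 40% DLT rate, with no DLT possible from escalators:

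- P(0) = 0.6^6 = 0.047; P(1) = 6 × 0.4 × 0.6^5 = 0.187; P(2) = 15 × 0.4² × 0.6^4 = 0.311; P(3) = 20 × 0.4³ × 0.6³ = 0.276
- starters only, at least 2 of 6: 1 − 0.047 − 0.187 = 0.767 from unrounded terms
- three escalators added, at least 3 of 9: 0.767 − 0.311 = 0.456
- six escalators added, at least 4 of 12: 0.456 − 0.276 = 0.179 from unrounded terms

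Section 3.3 lets the PI treat other events of concern as DLTs. If escalators could be assigned DLTs in that way at 10%, the last two figures would be 0.545 and 0.347. These numbers describe a reading that the text permits but does not state.

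**The case against.** **Might this change the MTD?** A reader might infer that counting escalators at both levels dilutes the DLT rate and lets level 2 pass as the MTD, with 2/6 turning into 2/9 or 2/12. The documents do not support that. Section 3.2.1 limits double counting to the safety analysis; 3.3 and 9.1.2 keep escalators out of the DLT count; and two DLTs fail the MTD criterion at any denominator. Timing also works against it: nobody may escalate into level 2 until it is declared safe. Two DLTs and escalators could coexist only if level 2 cleared on its first three patients and the DLTs came in starters enrolled later. That sequence is possible, since the MTD needs at least six patients. Even then the result would be two rules in 3.5 giving different answers, not a wrongly accepted dose.

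**Is the direction known?** No. Section 5.2.5.3 notes that AEs may appear several months after the last dose, and 3.4 is concerned with cumulative toxicity. Level-1 exposure could produce events recorded at level 2. Selection on Grade 1 or lower AEs makes understatement the likelier direction, but that is a judgement.

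**Does it matter for a descriptive table?** The tables are descriptive, 9.6.2 rules out formal testing of AE rates, by-patient listings cover deaths, SAEs and withdrawals due to AEs, and the Safety Monitoring Committee sees a summary of each level. All of that stands, and no error rate is affected. It does not settle the point, because dose selection under 3.5 draws on the safety data themselves.

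**Is tabulating by starting level cost-free?** Not if done alone: it would put events that arose at level 2 under level 1. This stands, and is why post-escalation events need their own column.

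**Conclusion.** The point holds for the by-level AE summaries. Followed as written, the plan produces a level-2 column confounded by selection for tolerance and by prior exposure, with no rule for AEs that span the dose change. Understatement for a new starter is probable but not shown. Its size is unknown; the 10 to 15 percentage points in the 40%/10% illustration rest wholly on assumed rates and on three to six escalators. The effect would be largest in the escalation-phase tables and much smaller after a full expansion at the same level.

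The DLT analysis set and the MTD count are already protected. What remains on the decision side is an undefined denominator in the one-third rule. Section 3.5 adds to the uncertainty by saying that all enrolled participants are considered in the DLT analysis, which is wider than 9.1.2.

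**What to change.** - **Sections 3.2.1 and 9.6.1:** report the by-level AE tables for patients who started at each level. Show AEs arising after intra-patient escalation in a separate column, with exposure time at the higher level.
- **Section 9.6.2:** state how an AE that begins before the dose change and continues, worsens or recurs after it is assigned, and how the once-per-term rule applies across the two columns.
- **Section 3.5:** state that the one-third rule uses the DLT analysis set of 9.1.2, so that escalators are not in the higher level's denominator, and reconcile the sentence on all enrolled participants with that set.

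The cost is wording, one extra table column and smaller numbers per column. No data are lost, and sample size, alpha and power are unchanged.
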